16.3 Analysis Populations

The following analysis populations will be defined for the study:

ITT Population – The ITT population will consist of all subjects who have signed informed consent, been enrolled in the study, and have had a successful placement of the BioWick SureLock implant.

Safety Population – The safety population will consist of all subjects who have signed informed consent, been rolled in the study and have had a procedure during which placement of the BioWick SureLock implant was attempted, whether or not placement was successful.

The primary analysis population for all primary and secondary endpoints will be the ITT population. The primary analysis population for safety will be the safety population.

16.4 Analysis Subgroups

Analysis subgroups may include age group.

16.5 Statistical and Analytical Plans

16.5.1 Primary Endpoint Analyses

Implant survivorship for each subject will be determined by whether the subject undergoes a revision or reoperation of the study device. Survivorship will be assessed using a Kaplan-

Meier analysis. Data will be considered right-censored for all patients that do not have a device failure. For patients lost-to-follow-up, their last available clinical visit will be used as the censored date. For patients that die during the study, their death date will be used as the censored date. The survivorship point estimate and 95% confidence interval about the point estimate will be calculated for the one-year primary endpoint.

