12.3 Subject Withdrawal

Subjects may discontinue from the study at any time. A subject may be discontinued from the study for the following medical or administrative reasons:

- **Subject Withdrawal of Consent** - Subjects will be free to discontinue from the study at any time and for any reason but must notify the study site of their exit from the study.
- **Adverse Event** – If during the procedures the subject suffers an AE that, in the judgment of the PI, Sponsor or medical monitor, presents an unacceptable consequence or risk to the subject, the subject will be discontinued from further participation in the study.
- **Lost to Follow Up** – Subjects discontinue from the study without notifying the study site.
- **Serious Protocol Violation** – If, during enrollment in the study, the subject fails to follow, violates or refuses to participate in any of the procedures described in the protocol then the subject will be discontinued from the study at the discretion of the Sponsor. If, at any point during the study, a subject is determined to have been erroneously enrolled into the study, the subject will be discontinued from the study due to protocol violation.
- **Other** - If the above reasons are not applicable, “Other” will be selected as the option and the appropriate reason for subject withdrawal provided.

For subjects who discontinue or are withdrawn from the study for any reason, the PI will notify the Sponsor and attempt to recover the following:

- AE occurrences since the last visit to the study site
- Concomitant medication usage since the last visit to the study site

If the subject is withdrawn at a study visit, the procedures for an early termination visit will be conducted to assess their continued well-being.

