13.5.6 Coronavirus (COVID-19) Expectations

If subjects are not allowed at the clinic for visits or if subjects refuse to come into the clinic due to COVID-19, then the following tasks should take place:

- Subject questionnaires (VAS, ASES, and VR-12) will be mailed to the subject for completion. These questionnaires should not be completed via phone. If the site does not receive a response from the subject, the site must attempt to contact the subject

and/or re-mail the subject questionnaires at least three (3) times within the visit window before submitting a protocol deviation, unless a response is received.

- The site will attempt to contact the subject to inquire of adverse events that may have occurred and/or been resolved since their last visit. The site is required to perform at least three (3) contact attempts to obtain this information. These contact attempts must be documented in the subject's study binder. If there is no response by the end of the visit window, a note-to-file (NTF) must be added to the subject's study binder indicating new adverse events were not confirmed for the visit.
- ROM measurements will not be required; however, a protocol deviation must be submitted.
- Label protocol deviations as being related to COVID-19, as applicable

Please note that these expectations are *specifically* for COVID-19 situations. If a subject misses a visit unrelated to COVID-19, this section does not apply and a "Missed Visit" protocol deviation will be submitted.

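### Section 16.5.1 ends a lost subject's event-free time at the last clinical visit but does not tie failures to visits; read literally, this lowers 12-month survivorship modestly

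*Combined protocol and SAP*

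**What the plan says.** All references are to the combined protocol and SAP.

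- **Event (16.5.1).** "Implant survivorship for each subject will be determined by whether the subject undergoes a revision or reoperation of the study device". The source of the information is not restricted.
- **Who is censored (16.5.1).** "Data will be considered right-censored for all patients that do not have a device failure".
- **Censoring date (16.5.1).** "For patients lost-to-follow-up, their last available clinical visit will be used as the censored date". Deaths are censored at the date of death, so the plan already accepts an off-visit date in one case. No date is given for subjects who leave for other reasons.
- **Off-visit information, any discontinuation (12.3).** The PI attempts to recover, among other items, "AE occurrences since the last visit to the study site". Loss to follow-up is one of the listed reasons for discontinuation.
- **Off-visit information, COVID-19 (13.5.6).** "The site will attempt to contact the subject to inquire of adverse events that may have occurred and/or been resolved since their last visit". At least three attempts are required, and the mode of contact is not stated. The section is a contingency: "If a subject misses a visit unrelated to COVID-19, this section does not apply".
- **Missing data (16.6).** The primary endpoint analysis is described as complete case.

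**The concern.** Kaplan-Meier estimation needs censoring that does not depend on the outcome. Take a subject seen at 3 months, contacted around 6 months, and then lost. If the contact reports a reoperation at Day 150, Section 16.5.1 makes the subject a failure at Day 150. If it reports none, the same section, read literally, moves the censoring date back to the 3-month visit. The subject leaves the risk set early only when the news is good. Risk sets shrink while the later failures stay in, so estimated survivorship is too low.

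The rule feeds the only primary endpoint. The bias is systematic, so more subjects would not remove it.

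**Working it through.** **Inputs from the documents.** Section 16.2: one-year survivorship 85%, 59 evaluable subjects, 15% lost, 71 enrolled, half-width 10.7%. Table 7.1: visits at Days 1, 90, 180 and 365.

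**The plan's own figure.** The Wald half-width is 1.96 × √(0.85 × 0.15 / 59) = 9.1%, so 10.7% is not reproduced. Other standard intervals (continuity-corrected Wald, Clopper-Pearson, Wilson, log-log) give 9.1% to 10.0%. The inflation is in order: 59 / 0.85 = 69.4, and 71 covers it. This mismatch is a separate matter. The half-width serves here only as a yardstick, and 9.1% leads to the same conclusion.

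**Assumptions, not in the documents.** Loss is independent of failure. A lost subject's last clinic visit is equally likely to be Day 1, 90 or 180 (Day 1 taken as time 0). A share q of lost subjects is later reached, and their status is then known to Day 365. The base case has constant hazard, S(t) = 0.85^(t/365), so S(90) = 0.96072, S(180) = 0.92298 and S(365) = 0.85.

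**Formula.** Let F be the share of lost subjects whose last visit has passed: 1/3, 2/3 and 1 in the three intervals. Under the literal rule, a reached subject past that visit stays in the risk set only if a failure is coming before Day 365, which has probability S(t) − 0.85. Per enrolled subject:

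- at risk: S(t) × [1 − 0.15F(1 − q)] − 0.15 × 0.85 × F × q
- failure rate: −S′(t) × [1 − 0.15F(1 − q)]

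The estimated hazard is therefore −S′ / (S − c), with c = 0.1275Fq / [1 − 0.15F(1 − q)]. The Kaplan-Meier factor from a to b is (S(b) − c) / (S(a) − c). If event-free contact also extends follow-up, c = 0 and the product is 0.85, with no bias.

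| q | c in the three intervals | Product of factors | Shift |
|---|---|---|---|
| 25% | 0.01104, 0.02297, 0.03592 | 0.96028 × 0.95976 × 0.91773 = 0.8458 | −0.42 points |
| 50% | 0.02179, 0.04474, 0.06892 | 0.95984 × 0.95880 × 0.91455 = 0.8417 | −0.83 points |
| 100% | 0.0425, 0.085, 0.1275 | 0.95898 × 0.95691 × 0.90826 = 0.8335 | −1.65 points |

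**Sensitivity.**

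- Early-weighted failures, S(t) = 0.85^√(t/365), so S(90) = 0.92247 and S(180) = 0.89214: −0.33, −0.66 and −1.31 points for q = 25%, 50% and 100%.
- Survivorship of 95%, constant hazard, 15% lost: −0.15 to −0.62 points.
- Survivorship of 85%, constant hazard, 30% lost and all reached: −3.82 points.

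A simulation of the same scenarios (8 runs of 20,000 subjects each) agrees. It gives −0.42, −0.83 and −1.65 points with constant hazard, and −0.32, −0.64 and −1.26 with early failures.

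**At trial size, with assumed counts.** Take 71 subjects with 2, 5 and 3 failures in the three intervals, and 11 lost subjects known event-free to Day 180.

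- Censored at last known status: (69/71)(64/69)(50/53) = 85.0%.
- Censored at the Day 90 visit: (69/71)(53/58)(50/53) = 83.8%.
- Censored at surgery: (58/60)(53/58)(50/53) = 83.3%.

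These are differences between estimates. They are bias only so far as failures among lost subjects were themselves learned off-visit.

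**The case against.** A reader might infer that the protocol routinely obtains implant status by phone and mail. It does not. Mail carries questionnaires only: "Subject questionnaires (VAS, ASES, and VR-12) will be mailed to the subject for completion". Phone is mentioned there only to be ruled out for them: "These questionnaires should not be completed via phone". Neither Section 12.3 nor Section 13.5.6 names implant status. That a reoperation would surface in an adverse-event inquiry is a reasonable inference, not a stated procedure.

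The term for the last visit is undefined. Section 13.5.6 works within visit windows and keeps the missed-visit deviation for absences unrelated to COVID-19, so a remote contact could be read as the visit itself. On that reading, the asymmetry through Section 13.5.6 disappears. Nor does any rule say what happens to a failure learned after a lost subject's last visit. That it counts follows from the unrestricted event definition.

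The affected group is narrow: subjects who left without notice and were nevertheless reached. Subjects who withdraw consent are a separate category, and the quoted sentence does not govern them. The study is single-arm with no performance goal, and the error would run against the device. If the complete-case wording of Section 16.6 excludes lost subjects altogether, their censoring date has no effect.

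All of this stands, and it reduces the point without removing it. Recovery under Section 12.3 is not limited to COVID-19 and includes lost subjects. The literal reading of Section 16.5.1 remains open to whoever programs the analysis.

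**Conclusion.** The point holds in a modest form. Read literally, Section 16.5.1 makes a lost subject's censoring date depend on the outcome of any later contact, and 12-month survivorship is then biased downward if loss is otherwise unrelated to failure. At the planning values the shift is about 0.3 to 0.8 points when 25% to 50% of lost subjects are reached. It reaches about 1.3 to 1.7 points only if every lost subject is reached. The contact rates, hazard shapes and visit timing are assumptions.

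Two stronger conclusions are not supported. One is that a shift of 1.3 to 1.7 points is what the trial should expect: that is the top of the range at 15% loss. The other is that the overall bias must be downward: if lost subjects who are never reached fail more often, survivorship would be overstated, and the documents give no figure for that. The effect is small beside the sampling uncertainty. The change is worth making because it is nearly free and concerns the primary endpoint.

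**What to change.** In Section 16.5.1, replace the censoring sentence for lost subjects with wording such as:

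> Subjects lost to follow-up or withdrawn without device failure are censored on the last date on which they were documented free of revision, reoperation or removal, by any route (clinic visit, remote contact or medical record). Failures are ascertained from the same sources.

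This also supplies a date for withdrawn subjects, and it includes removal, which Section 15.1.1 names.

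Ask about implant status explicitly at each contact under Sections 12.3 and 13.5.6, and record the date and route, so that nothing rests on inference from an adverse-event inquiry. In the same edit, reconcile Section 16.6 with Kaplan-Meier censoring; otherwise it is unclear whether lost subjects enter the analysis at all.

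The cost is one sentence in Section 16.5.1, one date field (with route) on the CRF, and the matching edit to Section 16.6. No further subjects or visits are needed.

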16.5.2 Secondary Endpoint Analyses

Summary statistics (mean, standard deviation, sample size, median, minimum, and maximum) will be computed for all quantitative secondary effectiveness endpoints on the raw and change from baseline data by time point. Frequency counts and percentages will be reported for all categorical secondary effectiveness endpoints.

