7. SCHEDULE OF STUDY EVENTS

Table 7.1 Study Flowchart of Scheduled Events

Event	Screening (Day -28 to -1)	Enrollment/ Visit 1 (Day 1) ¹	3 Months/ Visit 2 (Day 90 ± 14 Days)	6 Months/ Visit 3 (Day 180 ± 30 Days)	12 Months/ Visit 4 Or Early Termination Visit ² (Day 365 ± 30 Days)
Informed Consent	X				
Inclusion/Exclusion Criteria	X	X			
Medical History	X				
Physical Exam	X				
Concomitant Medications	X	X	X	X	X
BioWick SureLock Surgical Implantation		X			
Magnetic Resonance Imaging	X ³				
ASES Rating Scale	X		X	X	X
VR-12 Health Survey	X		X	X	X
ASES Range of Motion	X		X	X	X
Adverse Events	X	X	X	X	X
Subject Completion					X

¹ Upon meeting all I/E criteria, subjects will be enrolled on Day 1 after final confirmation of intra-operative I/E criteria.

² Assessments to be completed if the subject is an early withdrawal and returns to the clinic for a final visit.

³ A MRI scan obtained within 6 months of screening may be used to confirm I/E criteria. If a MRI scan is not available within this time frame, then a screening MRI scan is required.

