15.1.2 Secondary

The secondary endpoints of this study are:

- Implant survivorship at visit intervals other than 12 months
- VR-12 scores at 3 months, 6 months, and 12 months postoperative
- ASES rating scale at 3 months, 6 months, and 12 months postoperative
- VAS pain scores at 3 months, 6 months, and 12 months postoperative
- Range of motion (ROM) at 3 months, 6 months, and 12 months postoperative

The above endpoints based on continuous data will be reported as both raw and change from baseline (CFB) results.

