16. STATISTICAL ANALYSIS AND PLANNED ANALYSIS

16.1 Introduction

This study is a post-marketing, single treatment group, prospective study conducted at up to three study centers. The study will be conducted at as many as ten (10) centers in the U.S. Subjects will be enrolled in the trial for a period of 12 months. The objectives of the statistical analyses are to evaluate safety and effectiveness of the BioWick SureLock implant in the reattachment of soft tissue to bone in rotator cuff repairs.

A study center is defined as a hospital or medical office under the control and supervision of the Principal Investigator.

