16.2 Sample Size and Power

The study is sized with respect to the primary one-year survivorship endpoint of the study. Assuming an observed one-year survivorship of 85%, a total of 59 subjects is required in order to estimate the true survivorship within a 95% confidence interval with a half-width precision of 10.7%. This assumes a two-sided $\alpha=0.05$ level of significance and that the data come from a binomial distribution. In order to account for a 15% lost-to-follow-up rate, the sample size will be upwardly adjusted to 71 total subjects.

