16.6 Handling Missing Data

In the statistical analysis of the primary effectiveness endpoint of the study, only subjects with evaluable endpoint will be used in the statistical analysis, i.e., a complete case analysis.

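### The 12-month change in ASES, VR-12, VAS and ROM is summarised on observed cases only, with no interval and no use of dropouts' earlier scores; a repeated-measures estimate beside the table is a cheap improvement.

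*Combined protocol and SAP*

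**What the plan says.** The continuous secondary endpoints are VR-12, ASES, VAS pain and range of motion at 3, 6 and 12 months (section 15.1.2). All are also measured at screening as the baseline (section 13.5.1). Section 15.1.2 states: "The above endpoints based on continuous data will be reported as both raw and change from baseline (CFB) results".

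The analysis in section 16.5.2 is descriptive: "Summary statistics (mean, standard deviation, sample size, median, minimum, and maximum) will be computed for all quantitative secondary effectiveness endpoints", and this is done "on the raw and change from baseline data by time point". The only planned interval is in section 16.5.1, for survivorship: "The survivorship point estimate and 95% confidence interval about the point estimate will be calculated for the one-year primary endpoint".

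The only missing-data rule, section 16.6, is confined to the primary endpoint: "In the statistical analysis of the primary effectiveness endpoint of the study, only subjects with evaluable endpoint will be used". Nothing equivalent covers the secondary scores. The sample size is raised "In order to account for a 15% lost-to-follow-up rate" (section 16.2).

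Two other passages bear on which scores will exist:

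- Section 12.3 seeks adverse events and medication from every withdrawn subject. Scores are obtained only through an early-termination visit.
- Table 7.1 places that visit in the same column as the 12-month visit, with the footnote "Assessments to be completed if the subject is an early withdrawal and returns to the clinic for a final visit".

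**The concern.** With no rule for missing scores, each visit's summary rests on whoever attended. A subject who scores poorly at 3 or 6 months and then leaves contributes nothing to the 12-month change, although the baseline and earlier scores are in the database and predict the missing one. If such subjects leave more often than others, the 12-month mean change flatters the device. For ASES, VR-12 and ROM that means too large a gain; for VAS pain, too large a fall.

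Section 16.1 says "The objectives of the statistical analyses are to evaluate safety and effectiveness of the BioWick SureLock implant". In a single-arm study the 12-month change from baseline is the main functional evidence on effectiveness, even though survivorship is the primary endpoint. A reader would want it with an interval and with some protection against selective loss.

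**Working it through.** **Inputs from the documents.** 71 subjects, 15% loss, visits at baseline, 3, 6 and 12 months. The step from 59 to 71 roughly reproduces: 59 / 0.85 = 69.4, so 70 against the stated 71. Expected completers: 71 × 0.85 = 60.35, about 60. The plan gives no precision or sizing figure for the secondary scores, so there is none to reproduce.

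**Inputs assumed.** A 100-point scale, SD 18 at every visit, correlations between visits within 0.3 to 0.7, and loss before 12 months that follows a logistic model in the standardised 6-month score, set to 15% overall. Slopes of 1.2 and 2 per SD represent clear and strong dependence.

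**Step 1: bias of the observed-case mean change.** Let Z be the standardised 6-month score. Then

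bias = SD × [corr(6, 12 months) − corr(baseline, 6 months)] × E(Z among those retained).

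Numerical integration gives E(Z among those retained) = 0 for random loss, 0.073 at slope 0.5, 0.152 at slope 1.2 and 0.203 at slope 2.

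| corr(6, 12) − corr(0, 6) | Random loss | Slope 0.5 | Slope 1.2 | Slope 2 |
|---|---|---|---|---|
| 0.7 − 0.4 = 0.3, so 18 × 0.3 = 5.4 | 0 | 0.4 | 0.8 | 1.1 |
| 0.7 − 0.3 = 0.4, so 18 × 0.4 = 7.2 | 0 | 0.5 | 1.1 | 1.5 |

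Simulation with n = 71 and other correlation patterns in this range gave roughly 0.9 to 1.5 at 15% missing, in line with the last two columns. In SD units this is 0.9 / 18 = 0.05 to 1.5 / 18 = 0.08.

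**Step 2: compare with sampling error.** With a baseline-to-12-month correlation of 0.3, the SD of the change is 18 × √(2 × 0.7) = 21.3. The standard error with 60 completers is 21.3 / √60 = 2.7, and the 95% half-width is about 0.26 × 21.3 = 5.5 points. The bias is therefore about 0.9 / 2.7 = 0.3 to 1.5 / 2.7 = 0.6 of a standard error.

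**Step 3: a second route, free of the scale.** Completer bias = dropout share × (completer mean change − dropout mean change). At 15%, with an assumed difference in SDs of the change:

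| Assumed difference | Bias | Coverage of a nominal 95% interval (60 completers) |
|---|---|---|
| 0.25 SD | 0.04 SD | 94% |
| 0.5 SD | 0.075 SD | 91% |
| 0.75 SD | 0.11 SD | 86% |
| 1.0 SD | 0.15 SD | 79% |

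The step 1 range of 0.9 to 1.5 points is 0.9 / 21.3 = 0.04 to 1.5 / 21.3 = 0.07 SD of the change, which falls in the first two rows.

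**Step 4: what the earlier scores recover.** As a stand-in for the mixed model, regress the 12-month score on baseline, 3 and 6 months among those retained, predict for all 71, and subtract the baseline mean.

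- Loss driven by the 6-month score: bias is at most 0.1, with standard error about 2.6 against 2.7.
- Loss driven by the unseen 12-month score: observed-case bias is 1.9 to 2.6, and 1.4 to 2.0 remains. About three quarters is left (1.4 / 1.9 = 0.74; 2.0 / 2.6 = 0.77).

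**Step 5: early-termination scores, only if they were counted at 12 months.** If k such scores run d points lower and join 60 completers, the shift is k × d / (60 + k). For k = 2, d = 10 it is 20 / 62 = 0.3; for k = 7, d = 20 it is 140 / 67 = 2.1, in both cases downward. This is opposite in sign to the bias in step 1.

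**The case against.** The strongest case for the plan is that it matches its stated aim. Section 10.2 sets out to document effectiveness in a single-arm postmarket study, with no comparator, performance goal or test for these scores, and the study is sized on survivorship. Descriptive tables suit that aim, and the general statement in section 16.1 does not promise inference on secondary scores. This stands, and it is why the point is an improvement rather than an error.

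The size also rests on assumptions, is under one standard error, and vanishes if loss is unrelated to outcome. The mixed model does well in step 4 partly because the loss was generated in the way the model handles. Both remarks stand.

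Three stronger readings are tempting, and the documents do not support them:

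- A reader might infer that precision is hidden. It is not: the plan reports mean, SD and sample size, from which a t-interval can be rebuilt. That interval would still be centred on the completer mean.
- A reader might infer that the missing interval causes bias. It does not; the bias risk comes from handling missing scores by omission.
- A reader might infer from the shared column in Table 7.1 that early-termination scores are counted as 12-month scores. The table schedules procedures, its column carries the Day 365 ± 30 window, and section 16.5.2 summarises by time point. What is missing is an assignment rule.

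**Conclusion.** The point holds as a worthwhile, inexpensive improvement. As written, the 12-month mean change from baseline is an observed-case figure with no interval, and it makes no use of earlier scores from subjects who drop out. At the planned 15% loss it would be too favourable by roughly 0.9 to 1.5 points on a 100-point scale (0.05 to 0.08 SD) if subjects doing poorly at 6 months leave preferentially. It would be unbiased if dropout is random. The SD of 18, the correlations and the dropout mechanism are assumptions.

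The gain from a repeated-measures estimate is real but limited: it removes nearly all of this bias when loss depends on observed scores, and only about a quarter when loss depends on the unseen 12-month score. The handling of early-termination scores is a matter of missing detail only.

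**What to change.** 1. In section 16.5.2, keep the descriptive table. For each continuous secondary endpoint add the mean change from baseline with a 95% confidence interval, from a mixed model for repeated measures with baseline, 3, 6 and 12 months as visits and unstructured covariance. Show it beside the observed-case result, and state that the model assumes data are missing at random given the observed scores.
2. As a minor clarification, state that early-termination scores are assigned by actual study day and enter the 12-month summary only within the protocol's own window, Day 365 ± 30 (Day 335 to 395). Say also how a score outside every visit window is treated.

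The cost is a few lines of SAP text and a little programming on data already collected, with no new visits or subjects. The price in interpretation is the missing-at-random assumption. The model does not repair loss driven by the unseen 12-month outcome, and the report should say so. Both rules should be fixed before the scores are examined, since the study is open-label and section 16.7 allows an interim analysis at any time.
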